### **8.6.3 Stopping Rule for Platelet Count Results**

Stopping Rules for Platelet Count Results

Actions to be taken in the event of a low platelet count are summarized in [Table 3](#) below.

In the event of any platelet count less than  $50,000/\text{mm}^3$ , or a platelet count less than  $75,000/\text{mm}^3$  that occurs while the patient is already on reduced dose, dosing of the patient with Study Drug will be stopped permanently (Table 3). Platelet count will be monitored daily until 2 successive values show improvement then monitored every 2-3 days until platelet count is stable.

Administration of steroids is recommended for patients whose platelet count is less than  $25,000/\text{mm}^3$ . Recovery in platelet count may be accelerated by administration of high dose steroids. Treatment guidelines for immune thrombocytopenia (Provan et al. 2010) recommend Dexamethasone 40 mg daily for 4 days every 2-4 weeks for 1-4 cycles; Prednis(ol)one 0.5-2 mg/kg/d for 2-4 weeks then taper; or methylprednisolone 30 mg/kg/day for 7 days (**note:** may require continuation with oral steroids after methylprednisolone).

In the event of a platelet count  $< 75,000/\text{mm}^3$  and  $\geq 50,000/\text{mm}^3$ , and in the absence of major bleeding or clinically-relevant non-major bleeding (defined below; Schulman et al. 2005), dosing of a patient with Study Drug should be suspended temporarily until the platelet count has recovered to  $> 100,000/\text{mm}^3$ . If dosing is continued it must be at a reduced dose as shown in Table 3. The suitability of the patient for continued dosing will be determined by the Investigator in consultation with the Study Medical Monitor and will be based on factors such as the original rate of decline in the patient's platelet count, whether any bleeding events were experienced by the patient, and the speed of recovery of platelet count after interruption of dosing.

If, after reintroduction of Study Drug, the platelet count again falls below  $75,000/\text{mm}^3$ , then dosing of the patient with Study Drug will be stopped permanently.

Once a patient commences weekly monitoring this frequency of monitoring should continue until the platelet count returns to the normal range ( $\geq 140\text{K}/\text{mm}^3$ ) for 2 successive values.

Any unreportable platelet count result must be rechecked and determined not to have met a stopping rule before dosing can continue.

Definition of Major Bleeding Events (Schulman et al. 2005):

- Fatal bleeding, and/or
- Symptomatic bleeding in a critical area or organ, such as intracranial, intraspinal, intraocular, retroperitoneal, intraarterial or pericardial, or intramuscular with compartment syndrome, and/or
- Bleeding causing a fall in hemoglobin level of 20 g/L (1.24 mmol/L) or more within 24 hours, or leading to transfusion of 2 or more units of whole or red cells

Definition of Clinically-Relevant, Non-Major Bleeding Events (Schulman et al. 2005):

1. Multiple-source bleeding
2. Spontaneous hematoma  $> 25 \text{ cm}^2$
3. Excessive wound hematoma (not injection site related)
4. Macroscopic hematuria (spontaneous or lasting  $> 24$  hours if associated with an intervention)

5. Spontaneous rectal bleeding; epistaxis, gingival bleeding, hemoptysis, hematemesis
6. Bleeding after venipuncture for > 5 minutes

**Table 3 Actions in Patients with Low Platelet Count**

Platelet Count on Rx	Drug Dose	Monitoring
Normal range, $\geq 140\text{K}/\text{mm}^3$	No action	Monitor every 2 weeks
$\geq 100\text{K}$ to $<140\text{K}/\text{mm}^3$	No action	Closer observation Monitor every week*
$\geq 75\text{K}$ to $<100\text{K}/\text{mm}^3$	Permanently reduce as follows: For Cohort A: reduce to 10 mg every 4 weeks For Cohort B: reduce to 20 mg every 4 weeks For Cohort C: reduce to 30 mg every 4 weeks For Cohort D: reduce to 10 mg every 2 weeks For Cohort E: reduce to 10 mg every week	Closer observation Monitor every week*
$\geq 50\text{K}$ to $<75\text{K}/\text{mm}^3$	Pause dosing When platelet count returns to $> 100\text{K}/\text{mm}^3$ restart dosing as follows only if approved by Sponsor Medical Monitor: For Cohort A: reduce to 10 mg every 4 weeks For Cohort B: reduce to 20 mg every 4 weeks For Cohort C: reduce to 30 mg every 4 weeks For Cohort D: reduce to 10 mg every 2 week For Cohort E: reduce to 10 mg every week or Permanently discontinue Study Drug if it occurs while on already reduced dose	Closer observation Monitor every 2-3 days until 2 successive values show improvement Consider discontinuation of antiplatelet agents/non-steroidal anti-inflammatory drug (NSAIDS)/ anticoagulant medication
$\geq 25\text{K}$ to $<50\text{K}/\text{mm}^3$	Permanently discontinue Study Drug	Closer observation: Monitor daily until 2 successive values show improvement then monitor every 2-3 days until platelet count stable Discontinue antiplatelet agents/NSAIDS/anticoagulant medication while platelet count $< 50\text{K}/\text{mm}^3$ if possible

Platelet Count on Rx	Drug Dose	Monitoring
< 25K/mm 	Permanently discontinue Study Drug	
Closer observation: Monitor daily until 2 successive values show improvement then monitor every 2-3 days until platelet count stable
 
Steroids recommended** Consider need for hospitalization and referral to hematologist
 
Discontinue antiplatelet agents/NSAIDs/anticoagulant medication while platelet count < 50K/mm^3 if possible

\* Once a patient commences weekly monitoring this frequency of monitoring should continue until the platelet count returns to the normal range ( $\geq 140\text{K/mm}^3$ ) for 2 successive values.

\*\* Recovery in platelet count may be accelerated by administration of high dose steroids. Treatment guidelines for immune thrombocytopenia (Provan et al. 2010) recommend Dexamethasone 40 mg daily for 4 days every 2-4 weeks for 1-4 cycles; Prednis(ol)one 0.5-2 mg/kg/d for 2-4 weeks then taper; or Methylprednisolone 30 mg/kg/day for 7 days (note: may require continuation with oral steroids after methylprednisolone).

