### 8.8 Discontinuation of Study Drug

A patient must permanently discontinue study treatment for any of the following:

- The patient becomes pregnant. Report the pregnancy according to instructions in [Section 9.5.4](#)
- The patient withdraws consent
- The patient experiences an AE that necessitates permanent discontinuation of Study Drug
- The patient develops laboratory test abnormalities that meet any of the stopping rules listed in [Sections 8.6.1](#) to [8.6.3](#)
- When a platelet count of less than  $50,000/\text{mm}^3$ , or a platelet count less than  $75,000/\text{mm}^3$  while the patient is on a reduced dose.

The reason for discontinuation of Study Drug must be recorded in the electronic Case Report Form (eCRF) and source documentation.

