### **8.8.1 *Follow-up Visits for Early Termination from Treatment Period or from Post-Treatment Follow-up Period***

Any patient who discontinues early from the treatment period or from post-treatment follow-up period should be followed as per the platelet monitoring rules shown in [Table 3, Section 8.6.3](#) for the first 6 weeks post treatment period. Following this period, if the platelet count is stable (at least 3 consecutive values that are stable as determined by the Sponsor Medical Monitor and  $> 100,000/\text{mm}^3$ ), platelets should be tested 10 and 16 weeks post treatment period (as per visit schedule).

If a patient early terminates from the treatment period, an ET visit (Week 53 visit assessments) should be performed at the time of withdrawal, and ideally within 2 weeks from the last dose of Study Drug, and patients should start the 16-week post-treatment follow-up period to collect the study assessments in accordance with the Schedule of Procedures in [Appendix A](#).

If the patient early terminates from the post-treatment follow-up period, a final visit (assessments from the Week 16 of post-treatment follow-up period) should be performed at the time of withdrawal.

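### For a platelet count of 50K to <75K/mm³ on an already reduced dose, Section 8.6.3 requires daily counts but Table 3 requires them only every 2 to 3 days

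*Protocol*

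**What the plan says.** Section 8.6.3 names two triggers for a permanent stop in one sentence. The first is any count below 50K/mm³. The second is a count below 75K/mm³ "that occurs while the patient is already on reduced dose, dosing of the patient with Study Drug will be stopped permanently". The next sentence, in the same paragraph and not limited to either trigger, reads "Platelet count will be monitored daily until 2 successive values show improvement then monitored every 2-3 days until platelet count is stable". Section 8.8 also lists the two triggers together, the second again being a count below 75K "while the patient is on a reduced dose".

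Table 3 splits patients by count. Both rows below 50K carry the instruction "Monitor daily until 2 successive values show improvement then monitor every 2-3 days until platelet count stable", which matches the text. The row for ≥50K to <75K covers two kinds of patient: those whose dosing is paused, and those for whom the action is "Permanently discontinue Study Drug if it occurs while on already reduced dose". It has a single monitoring instruction for both: "Monitor every 2-3 days until 2 successive values show improvement".

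Section 8.8.1 says that patients who discontinue early "should be followed as per the platelet monitoring rules shown in" Table 3, Section 8.6.3, for the first 6 weeks after the treatment period. The step down to the week 10 and week 16 counts then needs "at least 3 consecutive values that are stable as determined by the Sponsor Medical Monitor", with the count above 100K.

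**The concern.** A patient at 50K to <75K on a reduced dose meets a stopping rule, and the protocol gives that patient two different monitoring schedules. The Table 3 schedule is the lighter one at both ends: it has no daily phase, and it stops at two improving values without continuing until the count is stable.

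This patient has fallen below 75K despite a lower dose. The interval to the next count determines how soon a further fall is seen. Below 50K it is an adverse event of special interest, and antiplatelet agents are to be stopped if possible. Below 25K steroids are recommended. Section 8.5.3 sends sites to Table 3 for the actions to take, so the lighter instruction is the one a site is likely to meet first. Section 8.12 asks for strict adherence to the platelet monitoring in Section 8.6.3, so a site that follows the row alone departs from the text.

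**Working it through.** There is no stated figure to reproduce. The check sets the two instructions side by side and counts the samples each requires.

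**Schedules by patient**

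| Patient | Section 8.6.3 text | Table 3 |
|---|---|---|
| Count <50K | Daily until 2 improve, then every 2–3 days until stable | Same |
| 50K to <75K, already on reduced dose (permanent stop) | Daily until 2 improve, then every 2–3 days until stable | Every 2–3 days until 2 improve |
| 50K to <75K, dosing paused | No frequency given in the text | Every 2–3 days until 2 improve |

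Text and table agree for the first trigger and differ for the second. Amendment 5 has the same mismatch, so it survived the Amendment 6 revision of the table ranges.

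**Counts required.** Day 0 is the index count.

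*(a) No improvement through day 6*
- Text: days 1, 2, 3, 4, 5, 6 = 6 counts.
- Row, 2-day step: days 2, 4, 6 = 3 counts. Row, 3-day step: days 3, 6 = 2 counts.
- First repeat: day 1 against day 2 or 3, a difference of 2 − 1 = 1 to 3 − 1 = 2 days.

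*(b) Values improve from the first repeat; stability not declared by day 14 (assumption)*
- Text, 2-day step after the daily phase: days 1, 2, 4, 6, 8, 10, 12, 14 = 8 counts, 4 of them by day 6.
- Text, 3-day step: days 1, 2, 5, 8, 11, 14 = 6 counts, 3 of them by day 6.
- Row alone: days 2, 4 or days 3, 6 = 2 counts, then nothing further from that row.
- Row with weekly monitoring already running: add 1 count (7 days after the last one, day 11 or 13), giving 2 + 1 = 3; or add 2 (fixed days 7 and 14), giving 2 + 2 = 4.

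An earlier declaration of stability shrinks the difference in (b). It does not affect (a).

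**The case against.** The strongest reply is that the daily sentence in Section 8.6.3 was meant only for counts below 50K and that Table 3 is right. Section 8.6.3 and Section 8.5.3 both refer to the table for the actions, and the table is organised by count. Its row names the reduced-dose patient and still gives 2 to 3 days. Section 8.8.1 can also be read as making the table govern after early discontinuation. This reading is possible, but the text does not state it: the sentence directly follows one that joins both triggers. If it was the intent, Section 8.6.3 is misworded and needs correcting instead. Section 8.8.1 leaves the conflicting sentence in place and directs sites to the lighter schedule.

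The second reply is that other safeguards apply:

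- Section 3.6: the relevant DSMB specialists are consulted within 24 hours when a stopping rule is triggered.
- Sections 6.2.1 and 8.5.3: every count below 140K raises an alert, with instructions within 24 hours where it is actionable.
- Section 8.5: a confirmatory sample is wanted promptly, ideally within 3 days.
- Section 8.5.3 and Appendix E: a one-time work-up, including a blood count, is triggered below 100K.

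These make it less likely that a site acts on the row alone, and they support a low severity. None of them requires daily counts, and the 3-day confirmation target is compatible with the table interval.

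The third reply is that the 14-day comparison in (b) isolates the row. That is fair. A patient whose dose was reduced for a low count will often already be on weekly monitoring until two successive values reach 140K, so 3 to 4 counts is the more realistic comparator. The 6-day comparison in (a) does not depend on this.

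**Conclusion.** The inconsistency is real and stands in the current text. For one subgroup that meets a stopping rule, the protocol prescribes daily counts in the text and counts every 2 to 3 days in the table. With a count that is not improving, that is 6 counts against 2 or 3 in 6 days, and a first repeat 1 to 2 days later. With an improving count it is 3 to 4 against 2 in 6 days. Over 14 days it is 6 to 8 against 2 from the row itself, or 3 to 4 with weekly monitoring running, assuming stability is not declared within that time.

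Severity is minor. The dosing action is identical in both places. The schedules are nested, so a site that follows the text also meets the table. Few patients are likely to be affected, although the protocol gives no figure for this. Neither the efficacy analysis nor the platelet-event incidence used for dose selection is affected. The mismatch itself is certain; which passage the sponsor intended is not. Daily counting is the cautious choice for a patient who fell below 75K despite a reduced dose.

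**What to change.** In the Table 3 row for ≥50K to <75K, separate the monitoring instruction by dose status. Patients already on a reduced dose, who are permanently discontinued, should follow the Section 8.6.3 schedule, as in the two rows below. Paused patients keep the present instruction. If the sponsor intended daily counts only below 50K, the sentence in Section 8.6.3 should be limited to that trigger instead; one of the two passages has to change.

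An optional clarification in the same row would say that paused patients, after two improving values, continue at no less than the weekly frequency of the milder rows.

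The cost is a wording amendment to one table row and a few extra local platelet counts in a small number of patients. Section 6.2.1 says local hematology results reach the site on the day of collection, so daily counts look feasible.

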### 8.7 Adjustment of Dose

Dose frequency adjustments for platelet count reduction must be made in accordance with [Section 8.6.3](#) and [Table 3](#) (above).

Other dose adjustments, including dose interruptions, and/or decreasing the dose will be allowed for safety or tolerability after consultation with the Sponsor Medical Monitor.

Patients may have their dose interrupted in response to AEs after consultation with Study Medical Monitor.

### 8.8 Discontinuation of Study Drug

A patient must permanently discontinue study treatment for any of the following:

- The patient becomes pregnant. Report the pregnancy according to instructions in [Section 9.5.4](#)
- The patient withdraws consent
- The patient experiences an AE that necessitates permanent discontinuation of Study Drug
- The patient develops laboratory test abnormalities that meet any of the stopping rules listed in [Sections 8.6.1](#) to [8.6.3](#)
- When a platelet count of less than  $50,000/\text{mm}^3$ , or a platelet count less than  $75,000/\text{mm}^3$  while the patient is on a reduced dose.

The reason for discontinuation of Study Drug must be recorded in the electronic Case Report Form (eCRF) and source documentation.

### **8.8.1 *Follow-up Visits for Early Termination from Treatment Period or from Post-Treatment Follow-up Period***

Any patient who discontinues early from the treatment period or from post-treatment follow-up period should be followed as per the platelet monitoring rules shown in [Table 3, Section 8.6.3](#) for the first 6 weeks post treatment period. Following this period, if the platelet count is stable (at least 3 consecutive values that are stable as determined by the Sponsor Medical Monitor and  $> 100,000/\text{mm}^3$ ), platelets should be tested 10 and 16 weeks post treatment period (as per visit schedule).

If a patient early terminates from the treatment period, an ET visit (Week 53 visit assessments) should be performed at the time of withdrawal, and ideally within 2 weeks from the last dose of Study Drug, and patients should start the 16-week post-treatment follow-up period to collect the study assessments in accordance with the Schedule of Procedures in [Appendix A](#).

If the patient early terminates from the post-treatment follow-up period, a final visit (assessments from the Week 16 of post-treatment follow-up period) should be performed at the time of withdrawal.

### **8.9 *Withdrawal of Patients from the Study***

Patients must be withdrawn from the study for any of the following:

- Withdrawal of consent
- The patient is unwilling or unable to comply with the protocol
- The patient meets any of the Exclusion Criteria (see [Section 5.2](#)) after enrolling in the study that in the opinion of the Investigator represents a safety risk to the patient

Other reasons for withdrawal of patients from the study might include:

- At the discretion of the Investigator for medical reasons
- At the discretion of the Investigator or Sponsor for noncompliance
- Significant protocol deviation

All efforts will be made to complete and report the observations as thoroughly as possible up to the date of withdrawal. All information, including the reason for withdrawal from study, must be recorded in the eCRF.

Any patient who withdraws consent to participate in the study will be removed from further treatment and study observation immediately upon the date of request. These patients should be encouraged to complete the ET visit (Week 53 visit assessments) and observations at the time of withdrawal ([Appendix A](#)).

For patients withdrawn for reasons other than withdrawal of consent every effort should be made to complete the ET visit (Week 53 visit assessments) and observations at the time of withdrawal ([Appendix A](#)).

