## 5.2 Exclusion Criteria

1. Within 6 months of Screening: acute coronary syndrome, major cardiac surgery, or stroke/transient ischemic attack
2. Within 3 months of Screening: coronary, carotid, or peripheral arterial revascularization, major non-cardiac surgery, or lipoprotein apheresis
3. Heart failure New York Heart Association (NYHA) class IV
4. Uncontrolled hypertension (systolic > 160 or diastolic > 100 mm Hg)
5. History of acute kidney injury within 12 months of Screening
6. Uncontrolled hyper or hypothyroidism
7. Active infection requiring systemic antiviral or antimicrobial therapy that will not be completed prior to Study Day 1
8. Known history of or positive test for human immunodeficiency virus (HIV), hepatitis C or chronic hepatitis B
9. Malignancy within 5 years, except for basal or squamous cell carcinoma of the skin or carcinoma *in situ* of the cervix that has been successfully treated
10. Patients with a history of major bleed or high-risk of bleeding diathesis
11. Recent history of, or current drug or alcohol abuse
12. Known history or presence of systemic allergic or pseudoallergic (drug) reactions

13. Hypersensitivity to the active substance or to any of the excipients
14. Clinically-significant abnormalities in screening laboratory values that would render a patient unsuitable for inclusion, including the following:
  - a. Urine protein/creatinine ratio (UPCR)  $\geq 0.25$  mg/mg. In the event of a UPCR above this threshold, eligibility may be confirmed by a quantitative total urine protein measurement of  $< 300$  mg/24-hr
  - b. Urine albumin/creatinine ratio (UACR)  $\geq 100$  mg/g. In the event of a UACR above this threshold, eligibility may be confirmed by a quantitative total urine albumin measurement of  $< 150$  mg/24-hr
  - c. Estimated GFR  $< 60$  mL/min (as determined by the Chronic Kidney Disease-Epidemiological Collaboration (CKD-EPI) Equation for creatinine clearance
  - d. Alanine aminotransferase (ALT) or aspartate aminotransferase (AST)  $> 2.0$  x ULN
  - e. Bilirubin  $> ULN$ , unless prior diagnosis and documentation of Gilbert's syndrome in which case total bilirubin must be  $\leq 3$  mg/dL
  - f. Alkaline phosphatase (ALP)  $> ULN$
  - g. Platelet count  $< LLN$
15. Use of warfarin, direct thrombin inhibitors or factor Xa inhibitors
16. Treatment with another investigational drug, biological agent, or device within 1 month of Screening, or 5 half-lives of investigational agent, whichever is longer

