## 8.5 Safety Monitoring Rules

Please refer also to the “Guidance for Investigator” section of the Investigator’s Brochure.

For the purposes of safety monitoring baseline is defined as the average of the pre-dose test closest to Day 1 and the Day 1 value itself.

In addition to the standard monitoring of clinical safety parameters, the following guidelines are provided for the monitoring of selected parameters chosen based on preclinical and clinical observations.

In case of discrepancy between the test results from 2 sources, such as between the central and local lab, safety-mandated action must be initiated based on the more critical (lower or higher, as relevant) of the 2 values.

**Confirmation Guidance:** At any time during the study (treatment or post-treatment follow-up periods), the clinical laboratory results meeting any of the safety monitoring criteria presented below **must be confirmed** by performing measurements (ideally in the same laboratory that performed the initial measurement) on new specimens prior to administering the next dose of Study Drug (ISIS 681257 or placebo). All new specimen collections should take place as soon as possible (ideally within 3 days of the initial collection).

In addition, as described in [Section 6.2.1](#) hematology labs should be sent in parallel to the central and local laboratory for analysis.

**Stopping Rule Guidance:** The Investigator may interrupt or permanently discontinue study treatment for any medical reason including changes in clinical laboratory results.

In the event of an initial clinical laboratory result that meets a stopping criterion, patients must not be re-dosed until a confirmatory test result has been reviewed by the Study Medical Monitor. If any of the stopping criteria described below (refer to [Sections 8.6.1](#) to [8.6.3](#)) are met and are confirmed, the patient will be permanently discontinued from further treatment with Study Drug (ISIS 681257 or placebo), evaluated fully as outlined below and in consultation with the Study Medical Monitor or appropriately qualified designee, and will be entered into the post-treatment evaluation portion of the study. In general, patients who do not meet the stopping rules based upon retest may continue dosing. However, the Investigator and the Study Medical Monitor (or appropriately qualified designee) should confer as to whether additional close monitoring of the patient is appropriate.

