### **8.6.2 Stopping Rules for Renal Function Test Results**

In the event of an estimated creatinine clearance (by CKD-EPI formula) meeting any of the following criteria, or any change in renal biomarkers deemed by the nephrologist on the DSMB to require further evaluation, a serum creatinine, urine culture, 24-hour urine sample for creatinine clearance and protein, and urine microscopy sample with inspection of sediment should be immediately obtained:

1. CKD-EPI decrease of > 40% from Baseline
2. CKD-EPI value < 45 mL/min/1.73 m^2

Dosing of a patient with Study Drug (ISIS 681257 or placebo) will be stopped permanently if 24-hour urine testing confirms any of the following values in the absence of an alternative explanation:

1. Urine protein is > 1.0 g
2. Creatinine clearance decrease of > 40% from baseline
3. Creatinine clearance < 45 mL/min/1.73 m^2

Irrespective of whether the stopping rule is confirmed or not, the follow-up schedule and frequency of renal function monitoring after the initial event will be determined by the Study Medical Monitor in consultation with the Investigator and the medical area specialist on the DSMB. The Investigator should consider consulting a local nephrologist for any change of renal function that presents a concern. If a renal biopsy is performed, a sample specimen should be made available for examination by an independent renal pathologist who has been engaged by the Sponsor to review such specimens.

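### Section 8.9 takes a patient out of the study, not only off study drug, when an exclusion criterion met after enrolment is judged a safety risk, and does not point to the Section 8.8.1 follow-up

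*Protocol*

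**What the plan says.** Section 8.9 opens with "Patients must be withdrawn from the study for any of the following". The list has three entries: withdrawn consent, inability or unwillingness to comply, and an exclusion criterion from Section 5.2 that is met "after enrolling in the study that in the opinion of the Investigator represents a safety risk to the patient". For patients who leave for a reason other than withdrawn consent, the section says that "every effort should be made to complete the ET visit (Week 53 visit assessments) and observations at the time of withdrawal". It does not mention Section 8.8.1 or the 16-week post-treatment period.

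Two exclusion criteria matter here. Criterion 10 reads "Patients with a history of major bleed or high-risk of bleeding diathesis" and carries no screening wording of its own. Criterion 14, which contains the platelet limit (14g), is introduced as "Clinically-significant abnormalities in screening laboratory values that would render a patient unsuitable for inclusion, including the following".

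Other sections treat a serious safety event as a reason to stop drug while follow-up continues:
- Section 8.5: a patient with a confirmed stopping-rule result stops drug and "will be entered into the post-treatment evaluation portion of the study".
- Section 8.6.3 and Table 3, for counts below 50,000/mm³: drug stops for good and "Platelet count will be monitored daily until 2 successive values show improvement then monitored every 2-3 days until platelet count is stable".
- Section 8.6.2: "the follow-up schedule and frequency of renal function monitoring after the initial event will be determined by the Study Medical Monitor", with the investigator and the relevant DSMB specialist consulted.
- Section 8.8: adverse events that require it, and stopping-rule results, end study treatment.
- Section 8.8.1: early terminators have the ET visit, platelet monitoring for 6 weeks, platelet tests at Weeks 10 and 16, and the 16-week follow-up.

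**The concern.** Sections 8.8 and 8.9 treat stopping the drug and leaving the study as different acts. The exclusion-criterion bullet sits under the second, with mandatory wording, although the situation it describes is one where further observation is most wanted. A patient with a major bleed on treatment can be placed under 8.8, which stops drug and leads to follow-up, or under 8.9, which withdraws the patient from the study and names only an ET visit. No sentence gives one section priority.

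If a site applied 8.9 alone, the patient would leave with much of the drug still present. The triggering event would be on record. A later, lower platelet nadir or a later renal or hepatic signal might not be. Those feed the safety endpoints in Section 10.1.3, which inform dose selection in Section 10.1.4.

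**Working it through.** The protocol gives no figure for this point, so the check compares texts and then sizes the loss per patient.

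**Tracing events through both routes**

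1. *Major bleed on treatment, no stopping-rule platelet count.* Under 8.8 (adverse event requiring discontinuation) and 8.8.1, drug stops, the ET visit is held and the 16-week follow-up begins. Under 8.9, criterion 10 plus a judgement of safety risk leads to withdrawal from the study, with an ET visit. The instructions differ.
2. *Platelet count below 50,000/mm³.* Sections 8.5, 8.6.3, Table 3 and 8.8 address this directly: stop drug, monitor closely, enter post-treatment evaluation. Criterion 14g is tied to screening values and does not clearly reach an on-treatment count. Only the high-bleeding-risk limb of criterion 10 could bring 8.9 in, against specific text that points the other way.
3. *Count from 100,000 to below 140,000/mm³.* Table 3 takes no dose action and asks for weekly monitoring. Not at issue.

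The tension is clearest in case 1, residual in case 2 and absent in case 3.

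**Scheduled observations missed by a patient handled under 8.9 alone** (Appendix A, footnote h; Section 3.4.3)

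- Platelet and urine renal biomarker checks: every 14 days for 6 weeks gives Weeks 2, 4 and 6; adding Weeks 10 and 16 gives 3 + 2 = 5.
- Clinic visits: Weeks 4, 10 and 16 = 3. These coincide with three of the five check times, so there are five distinct occasions, not eight.
- If the count is below 50,000/mm³, the daily and then 2-3 day counts of 8.6.3 come on top.

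**Drug still present**

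Inputs: terminal half-life h of 3 to 4 weeks (Section 2.3.4); ET visit ideally within 2 weeks of the last dose (Section 8.8.1). Assumptions: the visit falls at 2 weeks, the 16-week follow-up runs from it, and decline is single-exponential in the terminal phase. Fraction remaining = 0.5^(t/h).

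- ET visit, t = 2 weeks: 0.5^(2/3) = 0.63; 0.5^(2/4) = 0.71.
- End of follow-up, t = 2 + 16 = 18 weeks: 0.5^(18/3) = 0.016; 0.5^(18/4) = 0.044.

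The follow-up therefore covers the period in which terminal-phase drug falls from about 63-71% to about 2-4%. These figures describe the exposure window. They do not show that any patient is lost.

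**The case against.** The best defence is that 8.8.1 already answers the question. It covers any patient who discontinues early, refers to the same ET visit at the time of withdrawal, and then starts the 16-week follow-up. On that reading 8.9 lists reasons and 8.8.1 says what happens next. Section 8.9 itself helps: only patients who withdraw consent are expressly removed from study observation, and the paragraph on other withdrawals has no such clause. This stands, and it is why the conflict is partial.

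Other safeguards also stand. Section 9.5.1 has clinically significant laboratory abnormalities monitored back to baseline, or until the investigator and the sponsor's medical monitor agree to stop, and does not confine this to patients still in the study. Section 9.4.1 follows serious adverse events to resolution, though during the study period, which for an individual ends at the last study visit (Section 3.5). The triggering platelet drop is already counted in the Section 10.1.3 endpoint, and recovery is not a listed endpoint.

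The trigger can be contested too. The opening of Section 5 times eligibility within 4 weeks of Day 1 unless a criterion says otherwise, and Section 4.1 treats a patient as enrolled at consent, so the bullet has an ordinary use before dosing. However, its wording is not limited to that interval, and Section 3.1 speaks of enrolment at Day 1.

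A reader might infer that 8.9 orders every patient with platelets below 50,000/mm³, or any count below the lower limit of normal, out of the study. The documents do not support that: criterion 14 concerns screening values, specific text governs counts below 50,000/mm³, and the bullet also requires a judgement of safety risk.

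What remains is that 8.9 is mandatory and study-level, names only the ET visit and does not refer to 8.8.1, so the site must work out the reconciliation itself.

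**Conclusion.** The point holds as a partial inconsistency. For an exclusion criterion without screening-only wording, criterion 10 being the clear case, 8.9 requires withdrawal from the study, while 8.8 and 8.8.1 stop drug and keep the patient under observation. Where a stopping rule is also met, 8.5, 8.6.3 and Table 3 likewise continue follow-up.

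Loss arises only if a site applies 8.9 alone. The number of such patients is unknown and may be zero. It might be tempting to derive a count from the planning rate of 3.8% in Section 10.2, but that rate covers any drop below the lower limit of normal, not serious events, and says nothing about how sites would read 8.9. Nor does the text support a claim that the trial will lose safety data. The loss for an affected patient is five scheduled checks, three of them at clinic visits, plus any intensive counts not picked up through 9.5.1. The case for acting rests on the small cost of clarity and on how informative these few patients would be.

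**What to change.** In Section 8.9, change the exclusion-criterion bullet from withdrawal from the study to permanent discontinuation of study drug. Add that these patients, and others withdrawn for reasons other than withdrawn consent who are willing, have the ET visit and then the 16-week follow-up in 8.8.1. State that platelet, renal and hepatic results are handled under Sections 8.5 to 8.6 and Table 3. Section 9.5.4 already takes this approach for pregnancy, ending treatment while encouraging completion of follow-up.

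The cost is one wording change and, for any affected patient, a few follow-up visits already on the schedule. No new procedure is needed.
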